3.1.2 Dose Escalation

Participants will receive BMS-986253 A safety lead-in will be performed. The safety lead-in will be 28 days in length and consist of 2 doses of BMS-986253 (on days 1 and 15) with a safety evaluation through day 28. Dose escalation will proceed in cohorts of 3–6 participants. The MTD is the dose level at which no more than 1 of up to 6 participants experience DLT during one cycle (28 days) of treatment, and the dose below that at which at least 2 (of ≤ 6) participants have DLT as a result of the drug. If a participant did not experience DLT and did not finish treatment, he or she will not be evaluable for toxicity and will be replaced in the dose level. Participants will be taken off treatment if unacceptable toxicity occurs and is attributed to all therapeutic

agents (see section 3.8). These patients will also be evaluated for safety and efficacy (see Section 7.4.1 and 8).

Dose Escalation Schedule	
Dose Level	Dose of BMS-986253
Level -1	600 mg IV Q2W over 60 minutes
Level 1	1200 mg IV Q2W over 60 minutes ^a
Level 2	2400 mg IV Q2W over 120 minutes ^b
Level 3	3600 mg IV Q2W over 120 minutes ^b

^a 60 minute duration will be used for pts weighing > 35 kg. For pts weighing < 35 kg the infusion duration should be 120 minutes.

^b 120 minute duration will be used for pts weighing > 35 kg. For pts weighing < 35 kg the infusion duration should be 180 minutes.

Dose escalation will follow the rules outlined in the Table below.

Number of Participants with DLT at a Given Dose Level	Escalation Decision Rule
0 out of 3	Enter up to 3 participants at the next dose level
≥ 2	Dose escalation will be stopped. This dose level will be declared the maximally administered dose (highest dose administered). Up to 3 additional participants will be entered at the next lowest dose level if only 3 participants were treated previously at that dose.
1 out of 3	Enter up to 3 more participants at this dose level. 
 • If 0 of these 3 participants experience DLT, proceed to the next dose level. • If 1 or more of this group develop DLT, then dose escalation is stopped, and this dose is declared the maximally administered dose. Up to 3 additional participants will be entered at the next lowest dose level if only 3 participants were treated previously at that dose.
≤ 1 out of 6 at highest dose level below the maximally administered dose that exhibits optimal biologic activity	This is the OBD and is generally the recommended phase 2 dose. At least 6 participants must be entered at the recommended phase 2 dose.

The report including the supporting safety data and delineation of each criteria met, with the dose-escalation decisions will be provided to the Sponsor ([contact]) before additional participants will be enrolled into the study. The Dose Escalation Determination form on the sponsor website: <https://nih.sharepoint.com/:u/r/sites/NCI-CCR-OCD-Communications/SitePages/Forms-and-Instructions.aspx?csf=1&web=1&e=uWBXtI> may be used for this purpose.

Documentation of dose escalation determinations including the criteria met must be provided to the Sponsor prior to dose administration at the next dose level. An OSRO Dose Escalation Determination template form is available for recording of dose escalation related PI determinations or another format may be used but all equivalent information and PI signature is required.

The completed form or equivalent documentation should be kept in the site study files, sent to the Sponsor and available for review by the OSRO Clinical Site Monitors.

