1 INTRODUCTION

1.1 STUDY OBJECTIVES

1.1.1 Primary Objective

1.1.1.1 Phase I

- To determine the optimal biological dose (OBD) and recommended phase 2 dose (RP2D) of BMS-986253 in combination with and without DNMTi in participants with high- and low-risk myelodysplastic syndromes (MDS), respectively; and to describe the safety and tolerability of BMS-986253 in participants with MDS. OBD will be the lowest tolerated dose leading to maximal suppression of serum free IL-8 levels*.

*Maximal suppression of serum free IL-8 levels will be monitored for a goal of achieving IL-8 levels below the lower limit of detection of the assay in real time as outlined in Section **5.1.3.2** [ultrasensitive immunoassay based on Quanterix Simoa technology (lower limit of quantification = 0.86 pg/mL) by Myriad-RBM]

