3 STUDY IMPLEMENTATION

3.1 STUDY DESIGN

This study consists of two phases:

- Phase I: determination of OBD of BMS-986253 with and without DNMTi for HR- and LR-MDS cohorts, respectively, and
- Phase II: examining the efficacy of BMS-986253 with and without DNMTi for HR- and LR-MDS cohorts, respectively

In the Phase I, subjects will be enrolled to start treatment with BMS-986253 after a minimum of 2 cycles and up to initiation of an 8th cycle of DNMTi.

The safety endpoint will be DLT on D28. In addition, follow up for safety will be assessed 100 days after the last dose of treatment.

OBD will be the lowest tolerated dose level showing optimal biological activity, defined as maximal suppression of serum free IL-8 levels.

Participants enrolled on phase I will be treated at the corresponding BMS-986253 dose level until occurrence of disease progression, death, or unacceptable toxicity or until response assessment on C7D1 (maximum 6 cycles) if no evidence of clinical response. The participants will be followed up for overall, event- and progression-free survival until the study closure. The study will be closed when all enrolled participants have been followed up for at least 8 years or have died.

[figure not shown]
Both Phase I and II portions of study will enroll two cohorts:

A) HR-MDS: subjects with higher-risk MDS that will be treated with BMS-986253 in combination with DNMTi.

B) LR-MDS: subjects with lower-risk MDS that will be treated with BMS-986253 given as monotherapy.

In the Phase II portion, the treatment naïve subjects (or up to 4 cycles of prior DNMTi) will start treatment with BMS-986253 from the first cycle and the efficacy will be assessed until any off-treatment criteria are met (Section 3.8). BMS-986253 will be administered on days 1 and 15 of each cycle, and participants will remain on therapy until disease progression, death, or unacceptable toxicity or taken off therapy if no evidence of clinical response after 6 cycles (C7D1). The participants will be followed up for overall, event- and progression-free survival until the study closure. The study will be closed when all enrolled participants have been followed up for at least 5 years or have died.

Study treatment schema

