10 STATISTICAL CONSIDERATIONS

10.1 OBJECTIVES AND ENDPOINTS

OBJECTIVES	ENDPOINTS	JUSTIFICATION FOR ENDPOINTS
Primary		
Phase I: To determine OBD for BMS-986253 and RP2D, separately by cohort.	
 -Incidence of AEs, SAEs -AEs meeting protocol defined DLT criteria -AEs leading to discontinuation, death, and laboratory abnormalities. - OBD (RP2D) assessed during the first 30 days of treatment: - OBD will be the safest and lowest dose level showing optimal biological activity, defined as maximal suppression of serum free IL-8 levels.* 
*Maximal suppression of serum free IL-8 levels will be monitored for a goal of achieving IL-8 levels below the lower limit of detection of the assay in real time as outlined in Section 5.1.3.2 [ultrasensitive immunoassay based on Quanterix
	
standard endpoint for phase I protocol, see Section 3.1.1
 
Due to this being a targeted therapy, will pursue OBD instead of MTD as primary endpoint.

OBJECTIVES	ENDPOINTS	JUSTIFICATION FOR ENDPOINTS
	Simoa technology (lower limit of quantification = 0.86 pg/mL) by Myriad-RBM]	
Phase II: To determine efficacy as measured by overall response rate, separately by cohort.	-ORR per each cohort -assessed from first cycle until time of disease relapse, disease progression, or death, whichever occurs first, assessed every 3-6 months until 8 years.	Efficacy evaluation, standard for phase II protocol
Secondary		
Phase 1: To describe pharmacokinetic properties of BMS-986253 in MDS participants by cohort.	AUC, half-life, and steady state concentration Assessed during the first 30 days of treatment	Pharmacokinetic studies to evaluate for adequate absorption of therapy and define half-life/AUC and other properties of the study drug

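### The OBD row of the 3.1.2 escalation table takes the highest active level below the maximally administered dose, where sections 1.1.1.1, 3.1 and 10.1 define the OBD as the lowest

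*Combined protocol and SAP*

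**What the plan says.** Three sections define the OBD, and they agree:

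- Section 1.1.1.1: "OBD will be the lowest tolerated dose leading to maximal suppression of serum free IL-8 levels".
- Section 3.1: "OBD will be the lowest tolerated dose level showing optimal biological activity, defined as maximal suppression of serum free IL-8 levels".
- Section 10.1: "OBD will be the safest and lowest dose level showing optimal biological activity". Its justification column adds that the trial "will pursue OBD instead of MTD as primary endpoint".

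The decision table in section 3.1.2 turns the escalation data into a dose. Its last row applies to a level with at most 1 of 6 DLTs "at highest dose level below the maximally administered dose that exhibits optimal biologic activity", and calls that level the OBD and generally the recommended phase 2 dose, with at least 6 participants treated there.

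Two other rows say when a maximally administered dose exists. With two or more DLTs at a level: "This dose level will be declared the maximally administered dose (highest dose administered"). With 1 of 3 followed by one or more in the next three: "then dose escalation is stopped, and this dose is declared the maximally administered dose". After 0 of 3 the instruction is "Enter up to 3 participants at the next dose level". The planned levels are 1200, 2400 and 3600 mg, with 600 mg as level -1.

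Section 10.2 lets phase I participants treated at the OBD count in the phase II first stage. The higher-risk paragraph also says OBD. The lower-risk paragraph says MTD.

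**The concern.** The row and the definition differ in two ways. The row asks for the highest active level and the definition for the lowest. The row also limits the OBD to levels below the maximally administered dose, a limit that none of the definitions contains.

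Section 3.1.2 makes the table the operative rule and asks for the criteria met to be documented to the sponsor. The OBD is a phase I primary endpoint, is determined separately in each cohort, and generally becomes the phase II dose. A row that can contradict the primary objective, or exclude the top planned dose, leaves that decision open to argument once data are in hand.

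The case where every level is tolerated is not remote. Section 1.2.4.1 reports no DLTs with monotherapy or with nivolumab, although in solid tumours and without decitabine and cedazuridine.

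**Working it through.** **Step 1: what the maximally administered dose is when every level is tolerated.** Two readings are possible.

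- Reading (a): it is declared only after two or more DLTs, as in the two rows that declare it. With all levels tolerated none exists. After 0 of 3 or 1 of 6 at 3600 mg the table points to a next level that is not planned.
- Reading (b): the parenthesis glossing the term as the highest dose given makes a tolerated 3600 mg the maximally administered dose. *Below* then excludes 3600 mg.

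**Step 2: definition and row side by side.** Escalation is taken to start at Level 1 (1200 mg). *Tolerated* means at most 1 of 6 DLTs once filled.

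| Outcome | Levels meeting the IL-8 goal | Definition | Row, reading (a) | Row, reading (b) |
|---|---|---|---|---|
| All three tolerated | 1200, 2400, 3600 | 1200 | none named | 2400 |
| All three tolerated | 2400, 3600 | 2400 | none named | 2400 |
| All three tolerated | 3600 only | 3600 | none named | none (3600 excluded) |
| 3600 has 2+ DLTs, lower two tolerated | 1200, 2400 | 1200 | 2400 | 2400 |
| 3600 has 2+ DLTs, lower two tolerated | 2400 only | 2400 | 2400 | 2400 |
| 2400 has 2+ DLTs, 1200 tolerated | 1200 | 1200 | 1200 | 1200 |

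The third line matters because sections 1.2.4.2 and 1.2.4.3 cite modelling in which doses above 2400 mg may suppress IL-8 further. The fourth is possible but not expected: section 1.2.4.3 reports dose-dependent suppression, deepest at 2,400 mg every two weeks, so 1200 and 2400 mg tie only if both fall below the assay's detection limit.

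**Step 3: how often these situations arise, per cohort.** The plan gives no figure for this and no DLT rate for this population. The rate p is therefore an assumption, constant across levels, from 2% to 20%.

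Chance that a level passes: L = (1-p)^3 + 3p(1-p)^2 × (1-p)^3. At p = 0.10: 0.729 + 0.3 × 0.59049 = 0.9061.

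| p | L | All three pass, L^3 | 3600 mg also filled to 6, L^2 × [(1-p)^6 + 6p(1-p)^5] | 1200 and 2400 pass, 3600 has 2+ DLTs, L^2(1-L) |
|---|---|---|---|---|
| 2% | 0.9954 | 98.6% | 98.5% | 0.5% |
| 5% | 0.9734 | 92.2% | 91.7% | 2.5% |
| 10% | 0.9061 | 74.4% | 72.7% | 7.7% |
| 15% | 0.8138 | 53.9% | 51.4% | 12.3% |
| 20% | 0.7086 | 35.6% | 32.9% | 14.6% |

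The last column is an upper limit for the fourth line of Step 2 at each rate, because both lower levels must also meet the IL-8 goal. It also leaves out filling 2400 mg to 6. Requiring at most 1 of 6 there lowers 14.6% to 13.5%. If DLT rates rise with dose (5/10/20%), all three levels pass in 62.5% and 3600 mg alone fails in 25.7%.

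**Step 4: the lower-risk carry-over phrase.** The MTD in section 3.1.2 exists only below a level with at least two DLTs. If all levels are tolerated, the phrase in 10.2 describes no one. The six participants concerned are 6/12 = 50% of the lower-risk first stage and 6/25 = 24% of the final sample.

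**Step 5: the phase II designs are not touched.** The stated early-termination probabilities reproduce: P(X ≤ 2 of 12 at 20%) = 55.8% and P(X ≤ 5 of 15 at 30%) = 72.2%. Type I error and power are 0.0991 and 0.815 for the lower-risk design, and 0.0997 and 0.804 for the higher-risk design.

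**The case against.** The strongest reply is that three concordant definitions, none of which mentions a maximally administered dose, already settle the OBD, so the fault lies in one row. That stands. A reader might infer that the trial would have no OBD if every level is tolerated. The documents do not support this, because the definition names the lowest tolerated level with maximal suppression in that case too. Nor can it be said that the row necessarily names nothing there: on reading (b) it can name 2400 mg.

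It can also be said that the row is not applied mechanically. The OBD is only generally the recommended phase 2 dose, and the escalation report goes to the sponsor before further enrolment. That limits the harm but does not tell the sponsor which text governs.

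The direct conflict between lowest and highest is narrow, since it needs two tolerated levels that both meet the IL-8 goal. If one level is uniquely maximal, the two words pick the same dose, unless reading (b) excludes it. This also stands.

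On the MTD phrase, a reader might infer that the lower-risk first stage would be built on the wrong participants. The general rule earlier in 10.2 already admits those treated at the OBD who meet phase II eligibility, so this is a slip of wording.

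**Conclusion.** The row is wrong as written: a moderate to minor consistency fault, not a design failure. With 3600 mg too toxic and both lower levels tolerated and meeting the goal, it gives 2400 mg where the primary objective gives 1200 mg, on either reading. With all levels tolerated, it is silent on reading (a). On reading (b) it bars 3600 mg, even if only that dose is maximally suppressive, and prefers 2400 to 1200 mg when both meet the goal.

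The probabilities in Step 3 should not be read as the chance of a wrong dose. The 35.6 to 98.6% is how often the all-tolerated situation arises. The 0.5 to 14.6% caps the direct conflict under both readings at the assumed constant rates. How often several levels would meet the IL-8 goal cannot be derived from the documents. The textual conflict does not depend on any assumed rate.

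**What to change.** Replace the condition in the last row of the 3.1.2 table with: *the lowest dose level, up to and including 3600 mg, with at most 1 of 6 participants with DLT, that achieves maximal suppression of serum free IL-8; a candidate level with only 3 participants is filled to 6 before it is named.* Stating 3600 mg without a condition removes the dependence on how the maximally administered dose is read. A candidate that shows two or more DLTs on filling fails the condition, and the table's existing row for two or more DLTs applies. The requirement for at least 6 participants at the recommended phase 2 dose stays.

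In the lower-risk paragraph of 10.2, replace *that reached MTD* with *treated at the OBD and meeting phase II eligibility*, to match the general rule and the OBD wording of the higher-risk paragraph.

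The cost is one table row and one phrase. Filling to 6 fits the 18 per cohort already planned (3 levels × 6). The OBD definitions, sample sizes and Simon boundaries stay as they are.

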3.2 DRUG ADMINISTRATION

3.2.1 BMS-986253

Product Name	BMS-986253-01 Injection, 100mg/mL (1000 mg/vial OR 1200 mg/vial)
Product description and Packaging	
Packaging: Vials are labeled with a one panel clinical label. Individual vials are packaged into a labeled carton. Vials should remain in the original carton until use.
 
Vials: 20 cc Type I Glass Vial; with 20 mm seal
 
Appearance:
 
1000 mg/vial and 1200 mg/vial – Colorless to slightly yellow liquid (NGT Y5); Clear to opalescent (NGT 18 NTU); Light (Few) particulates (consistent in appearance to proteinaceous particles) may be present.

Product Ingredients	Each vial contains 1000 mg or 1200 mg of BMS-986253

3.2.1.1 Drug Product Preparation

Handling: As with all injectable drugs, care should be taken when handling and preparing BMS-986253. BMS-986253 should be prepared using local regulation/guidelines regarding engineering (e.g., a biological safety cabinet, laminar or vertical flow hood) and the administrative controls required for the preparation and administration of hazardous compounds (if so determined), to include standard procedures for the safe handling of sterile products applying aseptic techniques. Gloves are required. If BMS-986253 solution comes in contact with the skin or mucosa, immediately and thoroughly wash with soap and water. For additional information, please refer to the Safety Data Sheet (SDS).

Preparation:

- Withdraw the required volume of BMS-986253 and transfer into an intravenous container.
- Dilute BMS-986253 (1000 mg/vial or 1200 mg/vial) with either 0.9% Sodium Chloride Injection, or 5% Dextrose Injection to prepare an infusion with a final concentration ranging from 10 mg/mL to 16mg/mL (see table 3.1.2-1 below). BMS-986253 is compatible in polyolefin, PVC/non-PVC, DEHP/non- DEHP containers.
- Mix diluted solution by gentle inversion. Do not shake.
- Discard partially used vials or empty vials of BMS-986253.
- If using Close System Transfer Device (CSTD) for preparation and/or administration of BMS-986253 please check below list of compatible CSTD devices. Please reach out to us at [contact] for compatibility information on any other CSTDs.

Drug Product	Compatible CSTDs
BMS-986253, 1000 mg/vial	BD (Phaseal), ICU Medical (Chemolock and Chemoclave), B.Braun (OnGuard/Tevadaptor) and Equashield, Carefusion (Texium/SmartSite)

3.2.1.2 Recommended Storage and Use Conditions

The product does not contain a preservative. After preparation, store the BMS-986253 infusion either:

- at room temperature for no more than 4 hours from the time of preparation. (This includes room temperature storage of the infusion in the IV container and time for administration of the infusion.)

or

- under refrigeration at 2°C to 8°C (36°F to 46°F) for no more than 24 hours from the time of infusion preparation (including the maximum 4 hour RT storage period).

Do not freeze.

3.2.1.3 Dosage and administration

Administration: Visually inspect drug product solution for particulate matter and discoloration prior to administration. Discard the vial if the solution is cloudy, discolored, or contains extraneous particulate matter other than a few translucent-to-white, proteinaceous particles. Do not shake the vial.

BMS 986253 is to be administered as an IV infusion and not by IV push or bolus injection.

BMS-986253 infusion should be administered over protocol specified administration time through an intravenous line containing a sterile, non-pyrogenic, low protein binding polyethersulfone (PES) or Nylon in-line filter (pore size of 0.2). Do not co-administer other

drugs (outside of the ones listed in this protocol) through the same intravenous line. Flush the intravenous line “above” the in-line filter at end of infusion with appropriate diluent.

Dose level	Infusion total volume	Concentration	Rate duration
600 mg	50 mL	12 mg/mL	60 min
1200 mg	100 mL	12 mg/mL	60 min ^a
2400 mg	200 mL	12 mg/mL	120 min ^b
3600 mg	250 mL	14.4 mg/mL	120 min ^b

^a 60 minute duration will be used for pts weighing > 35 kg. For pts weighing < 35 kg the infusion duration should be 120 minutes.

^b 120 minute duration will be used for pts weighing > 35 kg. For pts weighing < 35 kg the infusion duration should be 180 minutes.

BMS-986253 should be dosed per subject assignment and as outlined in the study drug dosing section of the clinical protocol (See section [3.1.2](#)).

See BMS-986253 guidance document for specific instructions on dosing solution preparation and infusion duration.

See section [3.2.1.4.1](#) for Safety monitoring guidelines during first infusion of BMS-986253.

3.2.1.4 Infusion reactions

While rare, infusion reactions can occur with infusion of BMS-986253. Most infusion reactions if they occur are mild with symptoms ranging from local skin erythema, skin rash, flushing, headache, nausea, fevers, chills or shaking, itching, they can present as more severe reactions including hypotension, wheezing, dyspnea or hypoxemia, angioedema, facial swelling, dizziness or presyncope, which can be fatal if untreated. The onset and timing for these reactions include during or after the infusion on the day of infusion or the day after infusion, with resolution commonly 48 hours after onset of symptoms.

Monitoring for these symptoms of infusion reaction and prompt recognition with appropriate interventions is imperative and will be required on this protocol.

Management should be according to best medical judgment and up-to-date guidelines (for example by NCCN, available at

https://www.nccn.org/professionals/physician_gls/pdf/immunotherapy.pdf, ESMO[[103](#)]).

3.2.1.4.1 Safety Monitoring Guidelines for infusion of BMS-986253:

Vital signs, including blood pressure, heart rate, temperature, respiratory rate and SpO2 must be taken at the following intervals:

- For first hour of infusion: every 15 minutes.
- For second hour of infusion: every 30 minutes.
- Through one hour post-completion of infusion: every 30 minutes.

If participants experience any signs or symptoms of hypersensitivity, which include dyspnea, stridor, scratchy throat, throat or facial swelling, changes in vital signs including hypoxia hypotension, lethargy/confusion or change in mental status, immediate medical attention is needed with appropriate management per NIH Clinical Center Anaphylaxis Treatment Medication Guidelines (http://intranet.cc.nih.gov/pharm/pdf/ATM_GUIDELINES.pdf).

3.2.2 DNA methyltransferase inhibitors (DNMTi)

For HR-MDS cohort, the study drug of BMS-986253 will be given in combination with standard of care (SOC) FDA-approved DNMTi PO decitabine and cedazuridine according to guidelines outlined in FDA product label. SOC DNMTi will be administered via oral route once daily starting D2 of each treatment cycle through D6. [75][104][105]

